7 ADVERSE EVENTS

See CORE SOP012 AE Reporting for a description of the reporting of adverse events.

A number of conditions may result in temporary suspension until resolution. These include corneal infiltrates, corneal staining, limbal injection, bulbar injection or tarsal conjunctival abnormalities.

8 DISCONTINUATION FROM THE STUDY

Participants may be discontinued at the discretion of the investigator or sponsor in consideration of participant safety or protocol compliance, or at discretion of the participant. Participants discontinued from a study will be reimbursed \$20 per hour for their active involvement in the study (including the initial screening visit). Upon discontinuing, a participant will be offered the option of their data being withdrawn from future statistical analysis. The following is a list of possible reasons for discontinuation from the study:

- Screening failure: Participants will be discontinued if they do not meet the inclusion and exclusion criteria outlined in Section 4.2.3.
- Unacceptable performance with products to be used in study: Participants may be discontinued if they are unable to achieve acceptable comfort and /or vision with the study products.
- Positive slit lamp finding: Participants may be permanently discontinued from the study depending on the severity of the condition and on the judgement of the investigator.
- Adverse event: If a participant experiences an adverse event during the study they may be discontinued based on the clinical judgement of the investigator.
- Symptoms: If the participant has persistent symptoms they may be discontinued based on the clinical judgement of the investigator.
- Disinterest, relocation or illness: The participant may choose to discontinue due to reasons within or beyond their control.
- Violation of protocol or non-compliance: The participant will be discontinued if they are unable or unwilling to follow the protocol specified visit schedules and/or study procedures.
- Instillation of topical ocular medication: The participant will be discontinued if they elect to use a topical ocular medication during the study unless that topical ocular medication is prescribed for a limited duration (less than two weeks) to treat a transient condition; in this case the participant may remain an active participant (at the discretion of the investigator) after stopping topical ocular medication following resolution of the ocular condition).

- Lost to follow-up: The participant will be discontinued if they cannot be contacted and do not return for a final exit visit, and if the investigator has made a reasonable effort to contact the participant for a final study visit.
- Premature termination of the study by the sponsor, CORE or the Office of Research Ethics at the University of Waterloo.

A discontinuation form , stating the reason for discontinuation will be completed, which requires the signatures of both the participant and the investigator except where the participant is lost to follow-up in which case only the signature of the investigator is required.

All discontinuations including their reasons will be included in the final report.

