4.4.1 STUDY VISITS

A summary of the study visits is shown in Table 2.

Table 2: Summary of visits

Visit code	Day	Visits	Duration (hours)
V1	0	Screening	1.0
V2	0	Baseline & Dispense Provide instructions on at-home ratings.	0.5
Given to participant at V2	1, 7, 14±1	Subjective at-home ratings	0.5
V3 & Exit	14 + 2 after V2	Day 14 Follow-up	1.0
Total			3.0

Visits that fall outside of the specified visit windows will be designated as minor protocol deviations and at the end of the study, the data collected during protocol deviations will be assessed for their suitability to be included in the analysis data set.

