4.4.5 DAY 14 FOLLOW-UP VISIT AND EXIT, DAY 14+2 (VISIT 3)

Participants will attend the visit after 8 hours of DAILIES TOTAL1® study lens wear.

1. Collect unused study CLs;
2. Changes in medication history/medications;
3. Compliance with # of CL wear days/hour per day with typical # hours of digital device use over the past 2 weeks and for V3 visit day;
4. Collect and review at-home ratings;
5. logMAR distance HIHC VA with study lenses for OD, OS, and OU;
6. Subjective ratings (0-100 scales, where 100 means better performance; integer steps, both eyes rated together), to assess a typical day in the past 2 weeks 5 minutes after insertion, after 8 hours of digital device use, at the end of the day just prior to removal, and overall for:
 - *Comfort;*
 - *Dryness;*
 - *Clarity of vision.*
7. Subjective satisfaction;
8. Lens fit and surface evaluation:
 - *Lens centration;*
 - *Lens movement in primary gaze;*
 - *Lens tightness on push-up test;*
 - *Surface wettability and deposits.*
9. Biomicroscopy examination:
 - *External adnexa anomalies;*
 - *Cornea & anterior eye assessment for scars and infiltrates;*
 - *Bulbar & limbal redness;*
 - *Corneal & conjunctival staining with fluorescein dye;*

- *Palpebral conjunctival hyperemia & roughness.*

10. logMAR distance HIHC VA with habitual spectacles or CLs for OD, OS, and OU.

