4.4.6 STUDY EXIT

The study exit form will be completed when a participant exits the study. This form will be completed either at study completion, or if the participant is discontinued from the study at another time. A study exit form must be completed for all participants who have taken a study ID number. If, in the opinion of the investigator, post-study follow-up visits are required, the exit form will be completed after the last follow-up visit.

Exit monocular and binocular distance (HIHC VA logMAR) will be recorded with either the participant's spectacles, refraction or habitual contact lenses. An exit biomicroscopy assessment will be conducted if biomicroscopy has not already completed on the same day for a concurrent study visit.

After the exit assessments have been completed, the participant and investigator will complete the study completion and remuneration forms. At this time the participant will be considered as having exited the study.

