4.4.7 UNSCHEDULED VISITS

An unscheduled visit is defined as an interim visit requested by the participant or investigator due to an unanticipated problem. Data recorded at these visits will be entered into the database. Only relevant and applicable unscheduled visit information will be included in the final report as deemed necessary by the lead investigator.

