4.5.9 SUBJECTIVE RATINGS

Subjective ratings:

At visit 2, participants will be provided with subjective rating questionnaires using a 0-100 scale (where 100 = best performance; integer steps, both eyes rated together) to assess their first impression with the study CLs post-insertion regarding comfort and clarity of vision.

At the end of Visit 2, participants will be provided with at-home questionnaires to subjectively rate the experience with study lenses regarding comfort, dryness, and clarity of vision using a 0-100 scale (integer steps; both eyes together), where 100 means better performance. This questionnaire will be completed on Days 1, 7, and 14 ± 1 after Visit 2 (i.e. Day 0), at three different time-points on each of these days: after insertion, after 8 hours of digital device use, and at the end of the day just before lens removal. The final at-home questionnaire will be the evening before their scheduled Visit 3. In addition, times of lens insertion, first notice of discomfort, and lens removal will be collected. There will also be a diary entry for the number of hours of cumulative digital device use that day.

At Visit 3, participants will be provided with subjective rating questionnaires to assess a typical day over the past 2 weeks, to report their experiences i) 5 minutes after insertion, ii) after 8 hours of digital device use, iii) at the end of the day just prior to lens removal, and iv) overall. For each typical timepoint, comfort, dryness, and clarity of vision will be assessed using a 0-100 scale (integer steps; both eyes together), where 100 means best performance.

Satisfaction with study CL:

Satisfaction (5-point Likert scale: strongly disagree, slightly disagree, neither disagree or agree, slightly agree, strongly agree) with DAILIES TOTAL1® CLs overall and while using digital devices on a typical day in the past 2 weeks will be assessed for the following questions:

- *The study lenses provide good vision all day long.*
- *The study lenses provide good comfort all day long.*

- *I am satisfied with the comfort the study lenses provide when I use digital devices for ≥ 8 hours.*
- *I am satisfied with the vision the study lenses provide when I use digital devices for ≥ 8 hours.*
- *I don't experience eye strain when I wear the study lenses and use digital devices for ≥ 8 hours.*
- *I don't experience eye fatigue (tired eyes) when I wear the study lenses and use digital devices for ≥ 8 hours.*

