5 MONITORING PROTOCOL ADHERENCE

All personnel involved in this study will be listed on a delegation log and their training will be documented. Consent documentation will be reviewed by personnel not involved in the consent process. Visit windows will be reviewed when determining the analysis cohort. All adverse events and protocol deviations will be reviewed by the Lead Investigator. Serious and significant adverse events and major protocol deviations will be reviewed by the Principal Investigator and Head of Clinical Research.

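### The overall ratings and Likert items are taken only at Visit 3 and are not required from early leavers, so completer figures may look better than the experience of everyone dispensed.

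*Combined protocol and SAP*

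**What the plan says.** Section 2 defines the primary outcome as overall comfort, dryness and clarity of vision, each rated 0 to 100 and reported after two weeks of wear. Section 4.5.9 places the overall rating at the last visit: "At Visit 3, participants will be provided with subjective rating questionnaires to assess a typical day over the past 2 weeks". The Visit 3 list (4.4.5) agrees, and Table 3 marks the Likert satisfaction items in the Visit 3 column only.

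Section 8 lists reasons for leaving that bear directly on these outcomes. One is "Participants may be discontinued if they are unable to achieve acceptable comfort and /or vision with the study products". Another is "If the participant has persistent symptoms they may be discontinued based on the clinical judgement of the investigator". It also offers anyone who discontinues the option of having their data withdrawn from analysis, and requires all discontinuations and their reasons to appear in the final report.

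Section 4.4.6 covers early discontinuation as well as completion. Besides the form, it names two assessments: "Exit monocular and binocular distance (HIHC VA logMAR) will be recorded", and biomicroscopy if not already done that day. No rating is mentioned.

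Section 4.2.2 allows up to 35 dispensed, with a target of 32 completing. Section 10.1 promises descriptive statistics for the outcomes and binomial testing of the Likert items. It states no denominator and no treatment of a dispensed participant who has no Visit 3 rating.

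**The concern.** If someone stops because the lens is uncomfortable, blurred or causing symptoms, the plan as written can leave that person out of the means and agreement percentages that describe comfort, vision and symptoms. There is no second arm in which a similar loss might offset this. A rating not requested at exit cannot be recovered reliably afterwards.

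Four provisions might seem to close the gap, but none requires a rating from someone who never reaches Visit 3:

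- Section 4.4.1 says of out-of-window visits that "the data collected during protocol deviations will be assessed for their suitability to be included in the analysis data set", and section 5 adds "Visit windows will be reviewed when determining the analysis cohort". Both concern data that were collected.
- Section 4.4.7 says of unscheduled visits "Data recorded at these visits will be entered into the database", but lists nothing that must be recorded there.
- The at-home forms for Days 1 and 7 may exist for some leavers. They carry no overall item and no Likert item, and their return is listed only at Visit 3: "Collect and review at-home ratings".
- Reporting discontinuations with reasons makes the loss visible but does not alter the reported figures.

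Failures at lens fitting come before dispensing and are not part of this point.

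**Working it through.** **The plan's own figures.** Section 4.2.2 gives 35 − 32 = 3, so up to 3/35 = 8.6% of those dispensed could lack Visit 3 data if the ceiling of 35 is used and the target of 32 is just met. The plan states no dropout rate.

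**Inputs from the documents.** The threshold is 75 (section 3). I read it as applying to the mean itself, which section 3 does not specify. The earlier lens gave means and SDs of 91 ± 11 (comfort), 88 ± 11 (dryness) and 92 ± 9 (vision), and agreement or satisfaction of 81% to 91% (section 1). With that study's sample size of 32 (section 4.2.1), 81% to 91% corresponds to 26/32 to 29/32.

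**Assumptions not in the documents.** There are up to three performance-related leavers, with the leaver scores shown below. The Likert null proportion is 0.5, tested two-sided at 5%.

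**Likert percentages.** If x completers agree and k leavers are counted as not agreeing, x/(35 − k) becomes x/35. The drop is the completer rate × k/35.

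- k = 3: 26/32 = 81.3% becomes 26/35 = 74.3%, and 29/32 = 90.6% becomes 29/35 = 82.9%. The drop is 7.0 to 7.8 points.
- k = 2: the drop is 4.6 to 5.2 points at the same rates.
- k = 1: the drop is 2.3 to 2.6 points.

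The full three-leaver drop on a given item needs all three to have left for a reason bearing on that item.

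**Likert significance.** In the favourable direction, the exact test changes only at a count of 23 agreeing: 23/32 (p = 0.020) or 23/33 (p = 0.035) becomes 23/35 (p = 0.090). At 24 it holds: 24/32 (p = 0.007) becomes 24/35 (p = 0.041).

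**Means, leavers as the lowest raters.** This scenario simulates 35 normal ratings with mean 75 and SD 11, rounded and limited to 0–100, and removes the lowest k. The completer mean is then too high by 0.7, 1.3 or 1.8 points for k = 1, 2 or 3. Check for k = 3: the three lowest average 51.8, 56.4 and 59.1, and (35 × 75 − 51.8 − 56.4 − 59.1)/32 = 76.8.

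**Means, leavers at a fixed score L.** For the all-dispensed mean to reach 75 with three leavers, the completer mean must be at least (35 × 75 − 3L)/32.

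| Leaver score L | Completer mean needed |
|---|---|
| 60 | (2625 − 180)/32 = 76.4 |
| 50 | (2625 − 150)/32 = 77.3 |
| 25 | (2625 − 75)/32 = 79.7 |
| 0 | 2625/32 = 82.0 |

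**Means like the earlier lens.** With three leavers at 0, an arbitrary stress value, 32 × 88/35 = 80.5 and 32 × 92/35 = 84.1. Both stay above 75.

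**The case against.** The strongest reply is that little is at stake. Wear lasts about two weeks, in people who already wear lenses 13 or more hours a day and whose fit and acuity with this lens were accepted before dispensing. Thirty-five is a ceiling and 32 a target, not a forecast of three performance dropouts, and section 8 also lists illness, relocation, disinterest, non-compliance and loss to follow-up. The clause on unacceptable comfort or vision gives no timing and may partly describe fitting failures, so the persistent-symptoms clause is the cleaner support. The outcome is defined after two weeks of wear, and because discontinuations are reported, a reader could do the 26/32 against 26/35 arithmetic unaided.

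Most of this stands and limits the weight of the point. It does not remove it. Reported reasons allow a reader to guess at a leaver's answers, whereas asking at exit records them.

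Two stronger readings are tempting. A reader might infer that the study's conclusion against 75 is unsafe. The documents do not support that: the only rating means they give are 88 to 92, for another lens, and at those values the mean clears 75 even under the stress case. In the other direction, a reader might take the 0.7 to 1.8 point shift as a worst case, so that only a completer mean between 75.0 and 76.8 would matter. That holds only if leavers are the lowest draws from the same normal distribution as everyone else. People who stop because a lens is intolerable need not follow it, and the table gives thresholds up to 82.0. The SD of 11 is also borrowed from another lens with means near the top of the scale.

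**Conclusion.** The concern holds as a risk, not as a demonstrated bias. Nothing in the protocol requires the overall ratings or Likert items from a dispensed participant who leaves before Visit 3, although some listed reasons for leaving are closely tied to those outcomes.

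The effect on agreement percentages could be several points, up to 7 to 8 with three matching leavers. The comparison of a mean with 75 could change only if the completer mean lies fairly near that value; how near depends on leaver scores that nobody would have collected. All sizes rest on an assumed number of performance-related leavers, which may be zero. This is a minor improvement, worth making because it is cheap and must be set up before participants leave.

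A reader might also infer that the completer analysis is the wrong primary analysis. The documents do not support that, since section 2 defines the outcome after two weeks of wear.

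**What to change.** Leave the discontinuation rules as they are and make two edits.

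1. **Section 4.4.6.** At the exit visit of any dispensed participant who leaves early, give the overall ratings and Likert items with the recall period reworded to *since you started the study lenses*, because a two-week recall does not fit shorter wear. Collect any completed at-home ratings and record days of wear.

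2. **Section 10.1.** Keep the two-week completer result as primary. Beside it, report a sensitivity analysis in all dispensed participants:
   - Use early-exit ratings, labelled as taken after less than two weeks.
   - For a leaver without a rating, count 'not agree' only on Likert items that match the recorded reason: comfort or dryness items for comfort, vision items for vision, the matching symptom item for symptoms, and the overall performance item for any of these.
   - Do not impute the 0–100 ratings. Report the number missing, with reasons.
   - Do not use data that a participant has withdrawn.

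The cost is two short protocol edits and a few minutes per early exit. Early-exit ratings reflect shorter wear and so measure something slightly different, those lost to follow-up still contribute nothing, and the all-dispensed figures may be slightly less favourable.

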9 STUDY COMPLETION AND REMUNERATION

At the last scheduled protocol visit a study completion form will be completed, which requires the signatures of both the participant and the investigator. The participants will also be provided with a letter of appreciation.

Once their involvement in the study is complete, participants will be informed about receiving feedback following study completion in the Letter of Appreciation.

Participant remuneration will be \$60 for completing the study. This is calculated at \$20 per hour for the 2.5 hours of scheduled visits plus the 30 minutes of time required to complete the at-home ratings. Full details are given in the information consent letter. A cheque will be provided at the final visit.

10 STATISTICAL ANALYSIS AND DATA MANAGEMENT

10.1 STATISTICAL ANALYSIS

All data will be analyzed by CORE at the University of Waterloo. Unmasked data analysis will be conducted using Statistica, SPSS, or other appropriate software. Descriptive statistics will be provided on information regarding baseline variables (age, sex, refractive error distribution, etc.).

Descriptive statistics will be provided for all primary and exploratory outcomes as well as information regarding baseline variables (e.g. age, sex).

Subjective ratings and lens fit assessments will be compared between Visit 2 (Dispense) and Visit 3 (2-week follow-up) using either paired t-tests or Wilcoxon matched pairs, or using ANOVA, as applicable; statistical significance will be set at 5%. The appropriate tests will be

selected based on tests of normality – non-parametric tests will be used for data not showing a normal distribution. For assessments conducted for each eye separately, the right eye will be used for analysis if there is no difference between the eyes.

Binomial testing will be conducted to analyze Likert questionnaires. For example, agreement questionnaires (strongly disagree, slightly disagree, neither disagree nor agree, slightly agree, strongly agree) to determine whether participants had a positive or negative experience with the test lens.

Additional analysis may be conducted.

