2 OBJECTIVES

The objective of the study is:

- To refit habitual soft lens wearers, who use digital devices ≥ 8 hours on a typical day, with DAILIES TOTAL1[®] daily disposable CLs, and to assess their subjective ratings (0-100) for overall comfort, overall dryness, and overall clarity of vision during a typical day when using digital devices ≥ 8 hours while wearing DAILIES TOTAL1[®] CLs, reported after two weeks of wear.

The primary outcome variables for this study are:

- Subjective ratings (0-100, where 100=best) of overall comfort, overall dryness and overall clarity of vision with DAILIES TOTAL1® CLs during a typical day when using digital devices ≥ 8 hours (reported after two weeks of wear).

Other outcome variables of interest include:

- Likert type questions exploring the satisfaction with DAILIES TOTAL1® CLs when using digital devices (after two weeks of wear)
- Subjective ratings (0-100, 100=best) of comfort, dryness, and clarity of vision collected using an at home questionnaire on days 1, 7, and 14 ± 1 at three time-points each day: after lens insertion, after 8 hours of digital device use, and at the end of day
- Lens wear time
- Lens fit

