3 HYPOTHESIS

DAILIES TOTAL1® will provide a satisfactory performance for substantial digital device users as reflected in subjective ratings of ≥ 75 (0-100 scale, 100=best) for overall comfort, dryness, and clarity of vision during a typical day when using digital devices for ≥ 8 hours, reported after two weeks of wear.

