4.4.4 BASELINE AND DISPENSE, DAY 0 (VISIT 2)

1. Participants who successfully meet all the eligibility criteria will proceed directly to Visit 2, while continuing to wear the pair of study lenses that were just fit in Visit 1.
2. logMAR distance HIHC VA with study lenses for OD, OS, OU;
3. Subjective post-insertion ratings (0-100 integer scale, where 100 means best performance; both eyes rated together) to assess the initial impression of DAILIES TOTAL1® regarding:
 - *Comfort;*
 - *Clarity of vision.*
4. Lens fit and surface evaluation:
 - *Lens centration;*
 - *Lens movement in primary gaze;*
 - *Lens tightness on push-up test;*
 - *Surface wettability;*
 - *Surface deposits.*
5. At-home rating scales: Participants will receive at-home rating scales to be completed on Day 1, Day 7, and Day 14±1.
6. Lens wear instructions. The participants will be asked to:
 - *Wear the lenses at least 5 days per week and >13 hours per day throughout the study;*
 - *Complete the subjective at-home ratings to reflect their lens wear experience on Day 1 (the day after V2), Day 7, and Day 14±1 using a 0-100 scale. Ratings will be completed after insertion, after 8 hours of digital device use, and at the end of the day just before lens removal. The final at-home questionnaire will be*

completed the evening before their scheduled Visit 3. Variables to be assessed are:

- *Comfort;*
- *Dryness;*
- *Clarity of vision.*

- *Attend V3 after 8 hours or more of DAILIES TOTAL1® study lens wear.*

7. Dispense lenses.

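### The study's only hypothesis is a rating of at least 75 on three primary outcomes, but no analysis in section 10.1 compares any rating with 75

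*Combined protocol and SAP*

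**What the plan says.** - **Hypothesis (section 3).** The lens will perform satisfactorily, as shown by "subjective ratings of ≥ 75 (0-100 scale, 100=best) for overall comfort, dryness, and clarity of vision", for a typical day with at least 8 hours of device use, reported after two weeks.
- **Primary outcomes (section 2).** Under "The primary outcome variables for this study are" the protocol lists those same three overall ratings.
- **Collection.** At Visit 3 (section 4.4.5) comfort, dryness and clarity are rated for several times of a typical day, ending "at the end of the day just prior to removal, and overall for" the three attributes. Visit 2 (section 4.4.4) takes "Subjective post-insertion ratings (0-100 integer scale, where 100 means best performance; both eyes rated together) to assess the initial impression", and only for comfort and clarity. It has no dryness rating and no overall rating.
- **Analysis (section 10.1).** The primary outcomes are named only in the descriptive sentence: "Descriptive statistics will be provided for all primary and exploratory outcomes as well as information regarding baseline variables (e.g. age, sex". The tests are "Subjective ratings and lens fit assessments will be compared between Visit 2 (Dispense) and Visit 3 (2-week follow-up", by paired t-test, Wilcoxon or ANOVA at 5%, and "Binomial testing will be conducted to analyze Likert questionnaires". The section closes its analysis list with "Additional analysis may be conducted".
- **Sample size (section 4.2.1).** The 32 completers are carried over from an earlier study, with no test, SD or power given.

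**The concern.** The figure 75 appears as a rating threshold in section 3 and is not carried into section 10.1. The analysis section gives no one-sample test, no confidence limit set against 75, no proportion of participants reaching 75 and no rule for combining the three ratings. Followed as written, the plan would produce three means that someone then sets beside 75.

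This is an open-label, single-group study with unmasked analysis. If the success rule is chosen after the means are visible, a mean of 76 or 77 could be called support with no allowance for sampling error. The same data could also be read as group means or as individual ratings, and the two readings can give different answers.

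**Working it through.** **Does any planned analysis address 75?**

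1. Descriptive statistics cover the primary outcomes, but no summary is tied to 75 and no decision rule is given.
2. The Visit 2 versus Visit 3 tests ask whether ratings changed. A test of change would not address 75 even if both visits collected the same items. Separately, the overall ratings have no Visit 2 counterpart, so these tests cannot be applied to the primary outcomes at all.
3. The binomial tests are assigned to the Likert items, not to the 0-100 ratings.
4. The allowance for additional analysis specifies nothing.

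**Inputs for sizing the gap.** n = 32 (section 4.2.1). Means and SDs for another lens, from section 1: comfort 91 ± 11, dryness 88 ± 11, clarity 92 ± 9. The SD for this lens is not given, so I assume 11 and show 9 to 20. The sample size has no formula to reproduce. The 35 dispensed for 32 completers (section 4.2.2) allows for 3/35 = 8.6% loss.

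**Judging on the sample mean alone.** SE = 11/√32 = 1.945. P(sample mean ≥ 75) = Φ((true mean − 75)/SE):

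- true mean 75: Φ(0) = 50%
- true mean 74: Φ(−0.514) = 30%
- true mean 73: Φ(−1.028) = 15%

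**Judging on the lower limit of a two-sided 95% CI.** t(0.975, 31) = 2.040, and the observed mean must exceed 75 + 2.040 × SD/√32:

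| SD | SE | Half-width | Observed mean needed |
|---|---|---|---|
| 9 | 1.591 | 3.24 | 78.24 |
| 11 | 1.945 | 3.97 | 78.97 |
| 15 | 2.652 | 5.41 | 80.41 |
| 20 | 3.536 | 7.21 | 82.21 |

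A rating with true mean exactly 75 then passes 2.5% of the time under normality. In a skewed model (bounded beta-distributed integer ratings, SD 9 to 20) it passes 3.2% to 4.1% of the time.

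**Where the two rules disagree (SD 11, normal).** The chance that the mean reaches 75 but the lower limit does not is 68%, 47%, 15% and 2% at true means of 77, 79, 81 and 83. It is below 0.1% at 88.

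**At the other lens's values.** Lower limits: 91 − 3.97 = 87.03; 88 − 3.97 = 84.03; 92 − 3.24 = 88.76. All clear 75.

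**Mean or each participant.** At those same values, a normal approximation puts Φ(16/11) = 93%, Φ(13/11) = 88% and Φ(17/9) = 97% of participants at 75 or above. The chance that all 32 reach it is that proportion to the power 32: about 9%, 2% and 38%. The means pass easily, while an every-participant reading would probably fail.

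**The case against.** The best defence is that the study is descriptive. Section 2 aims to assess ratings, there is one group and no randomisation, and the sample size makes no power claim. No section promises a formal test of 75, and reported means show directly whether a benchmark is reached. This reading is tenable, so a formal test is not the only acceptable repair. It does not remove the gap, because section 3 is framed as a hypothesis and section 10.1 never says that 75 is only a benchmark or which summary it applies to.

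A second objection is that the choice of a two-sided 95% interval is mine. Section 10.1 sets 5% without sidedness; a one-sided 5% limit would move the SD 11 cut-off from 78.97 to 78.30. That is a small difference, but it should be fixed in advance.

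Three stronger readings are tempting and are not supported:

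- A reader might compute the chance that all three ratings pass when every true mean is 75 (12.5% on point estimates if independent, 1/8) and treat it as an error rate. True means of exactly 75 satisfy the hypothesis, so this is a boundary rate. It is also not the worst case for an all-three rule. That arises when one rating sits at 75 and the others lie well above, which returns the single-rating figures of 50% and 2.5%.
- A reader might infer that the missing rule would probably reverse the conclusion. Under the mean reading, the only means and SDs in the protocol point the other way, although they belong to another lens.
- A reader might say that section 10.1 expressly limits the primary ratings to description. It does not: its between-visit comparison refers to subjective ratings in general. The restriction follows from what Visit 2 collects.

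**Conclusion.** The point stands in limited form. No planned analysis compares the primary ratings with 75, and in practice the overall ratings receive descriptive statistics only. The plan does not say whether 75 applies to the mean or to each participant, nor whether it is a test or a benchmark.

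Under the mean reading, the consequence is confined to observed means between 75 and about 79 at SD 11 (78.2 at SD 9, 82.2 at SD 20). If results resemble those of the other lens, the conclusion would be the same under either rule. The numbers assume 32 completers, SDs borrowed from a different lens or assumed, and approximately normal means. Data collection is not affected. This should be fixed, but it does not undermine the study.

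**What to change.** In section 10.1, for each overall Visit 3 rating:

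- Report the mean with a two-sided 95% CI, and call the hypothesis supported only if all three lower limits exceed 75. No alpha split is needed, because all three must pass.
- If ratings are non-normal, use a bootstrap or other non-parametric interval, named in advance and in line with section 10.1's own rule for such data. A bootstrap keeps the mean as the target.
- Report the percentage of participants rating 75 or more, with an exact 95% CI, as supporting description.

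If 75 is meant only as a descriptive benchmark for the mean, say so, still report the intervals, and make no confirmatory claim.

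**Cost.** A few sentences, with no new data or participants. The lower-limit rule is stricter than a bare comparison: at SD 11, observed means between 75 and about 79 would no longer count as support. Power per rating is 80% at a true mean of 80.6. If all three true means were 80.6, the chance that all pass would be about 51% if independent (0.8³) and 68% at an assumed correlation of 0.8. The benchmark option avoids this loss but gives up the confirmatory claim.
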